### 6.6 Dose escalation and dose modification

Investigational dose adjustments and/or interruptions are not permitted.

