# 9 Discontinuation and completion

# 9.1 Discontinuation from study treatment and from study

# 9.1.1 Discontinuation from study treatment

Discontinuation of study treatment for a participant occurs when study treatment is permanently stopped for any reason (prior to the planned completion of study drug administration, if any) and can be initiated by either the participant or the investigator.

The investigator must discontinue study treatment for a given participant if, he/she believes that continuation would negatively impact the participant's well-being.

Discontinuation from study treatment is required under the following circumstances:

- Participant decision
- Pregnancy
- Any situation in which continued study participation might result in a safety risk to the participant
- Deterioration of PAH requiring hospitalization
- Development of heart failure symptoms consistent with pulmonary hypertension WHO Functional Class IV (symptoms at rest; severe symptoms at exercise)
- Lung transplantation required
- Atrial septostomy required
- Additional PAH directed therapy required beyond the scope of allowed concomitant medication Section 6.2.1) due to disease progression
- Adverse event that is graded severe by the investigator and considered study drug related
- If a liver or renal event occurs, follow guidelines outlined in Section 16.2 (Appendix 2) and Section 16.3 (Appendix 3) regarding discontinuation of study treatment.

If discontinuation from study treatment occurs, the investigator should make a reasonable effort to understand the primary reason for the participant's discontinuation from study treatment and record this information.

Participants who discontinue from study treatment agree to return for the end of treatment and follow-up visits indicated in the Assessment Schedule (refer to Section 8).

If the participant cannot or is unwilling to attend any visit(s), the site staff should maintain regular telephone contact with the participant, or with a person pre-designated by the participant. This telephone contact should preferably be done according to the study visit schedule.

After discontinuation from study treatment, at a minimum, in abbreviated visits, the following data should be collected at clinic visits or via telephone/email contact:

- New / concomitant treatments
- Adverse Events / Serious Adverse Events

The investigator must also contact the IRT to register the participant's discontinuation from study treatment.

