# 16.2 Appendix 2: Liver event and laboratory trigger definitions & follow-up requirements

To ensure participant safety and enhance reliability in determining the hepatotoxic potential of an investigational drug, a standardized process for identification, monitoring and evaluation of liver events has to be followed.

Please refer to Table 16-1 in Appendix 5 for complete definitions of liver laboratory triggers.

Once a participant is exposed to study treatment, every liver event defined in Table 16-1 should be followed up by the Investigator or designated personnel at the trial site, as summarized below. Since deterioration of PAH may result in increases of liver values it should be checked if an increase of liver values might be secondary to a deterioration of right heart failure. Liver chemistry tests (i.e. ALT, AST, TBL, PT/INR, ALP and G-GT) to confirm elevation. Increased liver values considered secondary to deterioration of right heart function are not considered liver events.

- 1. Liver chemistry repeats will be performed using the central laboratory. If results will not be available from the central laboratory, then the repeats can also be performed at a local laboratory to monitor the safety of the participant. If a liver event is subsequently reported, any local liver chemistry tests previously conducted that are associated with this event should have results recorded on the appropriate CRF.
- 2. If the initial elevation is confirmed, close observation of the participant will be initiated, including consideration of treatment interruption if deemed appropriate.
- 3. Discontinuation of the investigational drug (refer to the Discontinuation of study treatment Section 9.1.1 Discontinuation from study treatment), if appropriate
- 4. Hospitalization of the participant if appropriate
- 5. Causality assessment of the liver event
- 6. Thorough follow-up of the liver event should include, as per the investigator's discretion to allow for a causality assessment: serology tests, imaging and pathology assessments, hepatologist's consultancy; obtaining more detailed history of symptoms and prior or concurrent diseases, history of concomitant drug use, exclusion of underlying liver disease.

All follow-up information and procedures performed must be recorded as appropriate in the eCRF.

Table 16-1 Liver event and laboratory trigger definitions

	Definition/ threshold	
Liver laboratory triggers	ALT or AST > 5 × ULN	

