If ALT, AST and total bilirubin normal at baseline:	
 
ALP > 2 × ULN (in the absence of known bone pathology)
 
	
	
 
Total bilirubin > 3 × ULN (in the absence of known Gilbert syndrome)
 
	
	
 
ALT or AST > 3 × ULN and INR > 1.5
 
	

	
 
Potential Hy's Law cases (defined as ALT or AST > 3 × ULN and Total bilirubin > 2 × ULN [mainly conjugated fraction] without notable increase in ALP to > 2 × ULN)
 

	
 
Any clinical event of jaundice (or equivalent term)
 

	
 
ALT or AST > 3 × ULN accompanied by (general) malaise, fatigue, abdominal pain, nausea, or vomiting, or rash with eosinophilia
 

	
 
Any adverse event potentially indicative of a liver toxicity
 

If ALT or AST abnormal at baseline:	
 
ALT or AST > 3x baseline or > 300 U/L (whichever occurs first)
 

Notify Novartis study lead and medical lead of any finding of a liver event identified not explained by PAH worsening for further follow-up assessments.

Table 16-2 Follow up requirements for liver laboratory triggers - ALT, AST, TBL

	ALT	TBL	Liver Symptoms	Action
ALT increase without bilirubin increase:				
	If normal at baseline: ALT > 3 x ULN	Normal For participants with Gilbert's syndrome: No change in baseline TBL	None	No change to study treatment
	If elevated at baseline:  ALT > 2 x baseline or > 300 U/L (whichever occurs first)			
 
Measure         ALT, AST,         ALP, GGT,         TBIL, INR,         albumin, CK,         and GLDH in         48-72 hours.
 
Follow-up for         symptoms.
 

	If normal at baseline:  ALT > 5 x ULN for more than two weeks  If elevated at baseline:  ALT > 3 x	Normal For participants with Gilbert's syndrome: No change in baseline TBL	None	
 
Interrupt study treatment
 
Measure ALT, AST, ALP, GGT, TBIL, INR, albumin, CK,
 

	baseline or > 300 U/L (whichever occurs first) for			and GLDH in 48-72 hours.

Amended Protocol Version 03 (Clean)

	ALT	TBL	Liver Symptoms	Action
	more than two weeks			Follow-up for symptoms.
	If normal at baseline: ALT > 8 x ULN	Normal	None	
 
Initiate close monitoring and workup for competing
 

ALT increase with	bilirubin increase:			
	If normal at baseline: ALT > 3 x ULN	TBL > 2 x ULN (or INR > 1.5) For participants	None	

etiologies.

Study treatment can

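### Table 16-2 has no row for an asymptomatic ALT rise with bilirubin above normal up to 2 x ULN, so interruption is not mandated there, and Section 6.6 contradicts the interruptions that Appendix 2 does require

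*Protocol*

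**What the plan says.** Table 16-2 (Protocol, Section 16.2, Appendix 2) sets actions by ALT, TBL and symptoms.

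- **Block for ALT rises without a bilirubin rise.** All three rows require normal TBL and no symptoms. ALT > 3 x ULN means continued treatment and a retest in 48-72 hours. "ALT > 5 x ULN for more than two weeks" means "Interrupt study treatment". The third row is "If normal at baseline: ALT > 8 x ULN"; its action cell is broken in the extracted text.
- **Block for ALT rises with a bilirubin rise.** The asymptomatic row requires ALT > 3 x ULN and "TBL > 2 x ULN (or INR > 1.5". The other row is open to any TBL but requires liver symptoms. The actions printed beside these rows allow restart only once another cause has been found and enzymes are back at baseline, which presupposes that treatment was stopped.

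Table 16-1 counts "ALT or AST > 5 × ULN" as a trigger whatever the bilirubin. Steps 2 and 3 of Section 16.2 leave interruption or discontinuation to judgement, as does Section 10.2.1. Table 16-3 covers isolated bilirubin rises without defining the term.

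Section 9.1.1 requires discontinuation in "Any situation in which continued study participation might result in a safety risk to the participant" and otherwise refers back: "If a liver or renal event occurs, follow guidelines outlined in Section 16.2 (Appendix 2". Section 6.6 states: "Investigational dose adjustments and/or interruptions are not permitted".

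**The concern.** A stopping rule for liver injury should not become weaker as the liver profile worsens. Here prolonged ALT > 5 x ULN carries a mandatory interruption when bilirubin is normal, only discretion when bilirubin has begun to rise, and an implied interruption again above 2 x ULN. Section 16.2 says that a standardized process has to be followed, and the documents give no reason for this pattern, so it looks like a drafting gap.

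Section 6.6 adds a second difficulty. Where a table row orders an interruption, a site can argue that the specific rule prevails over the general one. In the gap no row does so, and a site that is unsure has a flat statement against interrupting.

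The stake is participant safety. Section 4.5 describes LTP001 as first-in-class and used until now only in healthy volunteers in Phase I. Here it is given daily for 24 weeks.

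**Working it through.** There is no plan figure to reproduce; the check is one of table coverage. The five Table 16-2 rows were written as conditions for a participant with normal baseline ALT and no Gilbert's syndrome, taking normal TBL as at most 1 x ULN. Where two rows match, the stricter is shown.

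**Asymptomatic, INR 1.0:**

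| TBL (x ULN) | ALT 4 x ULN, 3 weeks | ALT 6 x ULN, 3 weeks | ALT 9 x ULN, 1 week |
|---|---|---|---|
| 1.0 | continue, retest 48-72 h | interrupt (printed) | interrupt (a reading) |
| 1.01, 1.5, 2.0 | no row | no row | no row |
| 2.01 | interrupt (implied) | interrupt (implied) | interrupt (implied) |

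The ALT 9 entry at normal TBL assumes that the action cell is merged with the row above. With INR 1.6, or with symptoms, an interruption row applies at every ALT and TBL level tested in the table except that symptoms must be those listed. The gap is therefore confined to asymptomatic participants with INR at most 1.5.

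**What the other tables add in the gap:**

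- ALT > 5 x ULN: Table 16-1 is met. Section 16.2 then requires confirmation, close observation once confirmed, causality assessment, and sponsor notification if PAH worsening does not explain the event. Interruption is only to be considered.
- ALT > 3 to 5 x ULN: Table 16-1 also needs INR > 1.5, TBL > 2 x ULN, symptoms, or an adverse event suggesting liver toxicity. On the numbers alone it is not met.
- TBL > 1.5 to 2 x ULN: the lowest Table 16-3 row (> 1.5 to 3.0 x ULN) continues treatment but also requires liver tests to be repeated in 48-72 hours and then weekly. Whether it applies depends on the meaning of *isolated*.
- TBL > 1 to 1.5 x ULN: below the lowest numeric row of Table 16-3.
- Adverse event suggesting liver toxicity: the last row of Table 16-3 asks the site to consider interruption or discontinuation.

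So for ALT > 3 to 5 x ULN with TBL > 1 to 1.5 x ULN, no table sets a retest date. Section 8.4.1 requires repeat tests for laboratory adverse events but gives no interval.

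**Worst-case wait if no laboratory adverse event is declared.** On-treatment chemistry is due on Days 29, 57, 85, 113, 141 and 169, each with a +5 day window (Table 8-1).

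- Shortest gap: 57 - (29 + 5) = 23 days.
- Longest gap: (57 + 5) - 29 = 33 days.
- At normal TBL: 48-72 hours = 2 to 3 days.

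**Cost of one added interruption.** Active arm = 44 x 3/4 = 33; 1/33 = 3.0%.

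**The case against.** The case is narrow, and much of the safety net remains. At ALT > 5 x ULN the Table 16-1 follow-up runs in full. Below that, an investigator who judges the value clinically significant makes it an adverse event (Section 10.1.1), with mandatory repeats and possibly the liver-toxicity row. Discontinuation under Section 9.1.1 is stricter than interruption. PAH deterioration can itself raise liver values, and Section 16.2 excludes rises attributed to right heart deterioration, so leaving this band to judgement is defensible. Section 6.6 is a general line that the specific liver rules, expanded in Amendment 03, would ordinarily override.

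Most of this stands, and it limits the point. It does not restore the mandate: each fallback turns on judgement, and Section 9.1.1 sends liver events back to Section 16.2. The PAH confounder is present at normal bilirubin too, where interruption is nevertheless mandatory.

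Three stronger readings are tempting but unsupported:

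- That a participant already interrupted at normal TBL could resume once TBL rises. The restart condition, read as covering all the interruption rows, keeps that participant off drug.
- That Table 16-3 tells sites to keep dosing in the gap. In its ordinary sense *isolated* excludes ALT rises. If it does not, the same row also brings the 48-72 hour repeat and weekly tests.
- That 23 to 33 days is the expected wait. It is a worst case that needs the investigator to declare no laboratory adverse event.

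**Conclusion.** The point holds in limited form. What is missing is a mandate, not oversight. It concerns a participant who is not yet interrupted, has no symptoms or Gilbert's syndrome, has INR at most 1.5, and has TBL above 1 and up to 2 x ULN when ALT > 5 x ULN has lasted more than two weeks. The same probably holds for ALT > 8 x ULN. That extension, and the application of the restart condition to the normal-TBL rows, rest on reading the broken action column as one merged cell; the core finding does not.

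The contradiction between Section 6.6 and Tables 16-2 and 16-3 is separate and stands on the printed text.

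The documents do not allow an estimate of how many participants would fall in the gap, and no effect on the efficacy conclusions is claimed. The correction should be made because it concerns a safety rule and costs little.

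**What to change.** In an amendment:

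1. Make the Table 16-2 interruption rows (ALT > 5 x ULN for more than two weeks, with its elevated-baseline equivalent; ALT > 8 x ULN) apply at any TBL, and move them out of the block for ALT rises without a bilirubin rise. Keep the Section 16.2 exclusion for rises attributed to right heart deterioration.
2. Add a row for other asymptomatic ALT > 3 x ULN (or the elevated-baseline cut-off) with TBL above normal up to 2 x ULN, requiring the 48-72 hour retest and consideration of interruption.
3. State in Table 16-3 that *isolated* means no Table 16-2 ALT criterion is met.
4. Add to Section 6.6: *except as required by Appendix 2 or Appendix 3*.

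The cost is rewording. Retests use the test list already in Table 16-2. There may be a few more retests and interruptions, each interruption on LTP001 affecting 1 of about 33 active-arm participants.

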## Appendix 3: Specific Renal Alert Criteria and Actions and Event 16.3 Follow-up

Renal safety parameters will be checked at all visits. Careful monitoring of deterioration of renal function or of pathologic changes in the urinalysis is required. The below definitions mandate to classify a renal parameter deviation as a renal event. Further guidance for the followup of abnormal renal function parameters and renal events will be provided in the investigator portal under Renal Events guidance document.

#### **Table 16-4** Specific renal alert criteria and actions

## Serum Event

Serum creatinine Follow up within 1-2

days increase > 25% fold

compared to baseline Please review

Section 8.4.1

## **Urine Event**

New onset dipstick Follow up within 2-5

proteinuria ≥3+ OR days

New onset dipstick Please review hematuria ≥3+ (after Section 8.4.1

excluding

menstruation, urinary tract infection. extreme exercise, or

trauma)

## For all renal events:

Document contributing factors in the eCRF: co-medication, other co-morbid conditions, and additional diagnostic procedures performed

Monitor subject regularly (frequency at investigator's discretion) until either:

Event resolution: sCr within 20% of baseline or

Event stabilization: sCr level with ±20%

variability over last 2 months

Further recommendations on the follow-up for renal events can be found in the investigator portal (Follow-up for renal events document).

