## 10.2.2 Renal safety monitoring

Once a participant is exposed to study treatment, the following two categories of abnormal renal laboratory alert values should be assessed during the study period:

- Serum creatinine increase > 25% compared to baseline
- Any one of the following:
  - New onset dipstick proteinuria  $\geq 3+$ , OR
  - New onset dipstick hematuria  $\geq 3+$  (after excluding menstruation, UTI, extreme exercise, or trauma)

Abnormal renal event findings should be confirmed within 5 days.

Once a participant is exposed to study treatment, renal laboratory alerts or renal safety events should be monitored and followed up by the investigator or designated trial staff. Please see Table 16-4 for further guidance.

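### Table 16-4 ends follow-up of every renal event on serum creatinine alone, so a persisting 3+ proteinuria or hematuria event can count as resolved

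*Protocol*

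**What the plan says.** Protocol Section 10.2.2 sets two separate categories of renal alert. The first is "Serum creatinine increase > 25% compared to baseline". The second is new-onset dipstick proteinuria or hematuria of 3+ or more, with common benign causes of hematuria excluded. The urine category carries no creatinine condition. The same section adds: "Abnormal renal event findings should be confirmed within 5 days".

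Appendix 3 (Section 16.3) makes the classification compulsory: "The below definitions mandate to classify a renal parameter deviation as a renal event". It also states: "Careful monitoring of deterioration of renal function or of pathologic changes in the urinalysis is required". Table 16-4 repeats both event types, with follow-up in 1-2 days for the serum event and 2-5 days for the urine event.

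The block of Table 16-4 that covers all renal events then gives a single stop rule. The participant is monitored, at a frequency the investigator chooses, until one of two conditions holds. One is "Event resolution: sCr within 20% of baseline or". The other begins "Event stabilization: sCr level with ±20" and goes on to give a percentage variability over the last 2 months. Neither has a urine term. For further recommendations, Appendix 3 refers to a document in the investigator portal.

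**The concern.** The urine trigger is there to pick up renal findings that creatinine does not show, yet the rule that closes the event looks only at creatinine. Read as printed, a participant with confirmed 3+ proteinuria and unchanged creatinine has a renal event that is already resolved.

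At stake is whether the trial can tell a transient urine finding from a persistent one. LTP001 is first in class and, according to Section 4.5, has not been used outside a Phase I study in healthy volunteers. Section 9.1.1 sends investigators to Appendix 3 when a renal event occurs, so this text is what a site will apply. The liver appendix handles a comparable case better: for isolated bilirubin rises up to 10 times the upper limit of normal, Table 16-3 follows the liver tests themselves until they resolve or return to baseline.

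**Working it through.** The plan states no figure on this point. The check applies the rule to each event type and then counts the urinalyses that remain in the schedule.

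**Step 1. Closing rule against opening rule** (Section 10.2.2, Table 16-4). The check uses the resolution criterion; either criterion is enough to end monitoring.

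| Event | Opens when | Resolved when | Can resolution be met at detection? |
|---|---|---|---|
| Serum | creatinine more than 25% above baseline | creatinine within 20% of baseline | No. It must first fall by more than 25 - 20 = 5 percentage points of baseline |
| Urine | dipstick 3+ or more, any creatinine | creatinine within 20% of baseline | Yes, for any creatinine change from -20% to +20% |

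A urine event without a simultaneous serum event has creatinine no more than 25% above baseline. Within that group, only a rise of more than 20% and up to 25%, or a fall of more than 20%, fails the resolution criterion at detection. The dipstick result plays no part.

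**Step 2. What other text requires** (Sections 8.4.1 and 10.1.1).

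- Under Section 10.1.1 an abnormal laboratory value is an adverse event only if it causes signs or symptoms, is considered clinically significant, or requires therapy. Classification as a renal event is not on that list.
- If the finding is an adverse event, Section 8.4.1 requires repeats until it normalizes or loses clinical significance, and Section 10.1.1 requires follow-up until it resolves or is judged permanent. Those urine events are covered.
- If it is not an adverse event, Table 16-4 holds the only criteria in the protocol for ending renal event monitoring.

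**Step 3. Scheduled urinalyses left after first detection** (Table 8-1). Post-dose urinalyses fall on Days 29, 57, 85, 113, 141 and 169 (each +5 days) and Day 199 (±5 days), 7 in all.

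| First seen at | Week 5 | Week 9 | Week 13 | Week 17 | Week 21 | Week 25 | Week 29 (EOS) |
|---|---|---|---|---|---|---|---|
| Tests remaining | 6 | 5 | 4 | 3 | 2 | 1 | 0 |

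- On-treatment interval: 57 - 29 = 28 days nominal. With visit windows it runs from 57 - 34 = 23 to 62 - 29 = 33 days.
- Week 25 to EOS: 199 - 169 = 30 days nominal. With visit windows it runs from 194 - 174 = 20 to 204 - 169 = 35 days.
- Visits after which at most one test remains: 2 of 7, or 29%. This is a share of scheduled visits, not of events.

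The count assumes that the event is detected at a scheduled visit and that the participant does not enter the open-label extension. For those who do enter, Section 3 leaves replacement of the EOS procedures to the extension protocol, which was not available, so no tests are counted as lost.

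**The case against.** The strongest case on the other side is that little is left once the rest of the protocol is applied.

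- **The remaining group is small by construction.** It consists of confirmed 3+ findings that the investigator has considered, judged not clinically significant and documented as such. Even for laboratory adverse events, mandatory repeats stop once the result is no longer clinically significant, so asking for more here could be called a preference. This stands as a limit on size. It does not repair the rule, which labels the event resolved because of creatinine and not because of any judgment about the urine finding.
- **The urine row of Table 16-4 points to Section 8.4.1.** The renal follow-up row there lists UPCR, UACR, repeat urinalysis and sediment, in wording that is partly permissive and partly directive. Appendix 3 also requires careful monitoring of urinalysis changes. Neither text ties a urine result to closing the event.
- **Nothing closes at the moment of detection,** because the finding must be confirmed within 5 days. That is correct in practice: closure would come at confirmation. The resolution criterion is nonetheless already satisfied at detection.
- **The portal guidance may contain a urine criterion.** It may; it was not seen. The protocol describes it as further guidance and recommendations, which would not replace the protocol's own definition of resolution.
- **Having no test after the last visit is common to any finding that is not an adverse event.** This is fair. Nevertheless, the monitoring rule for renal events is what would otherwise carry follow-up past that visit, and for urine events it is already met.

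**Conclusion.** The concern holds, and it is minor. As printed, Table 16-4 treats a urine renal event with creatinine within 20% of baseline as resolved while the urine finding persists. The resolution criterion works as intended for serum events.

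The gap covers urine events not judged to be adverse events. For those found from Week 5 to Week 21, at least 2 further scheduled urinalyses give information whatever label the event carries. The main exposure is at Week 25 and EOS, 2 of the 7 scheduled post-dose urinalyses. The documents give no expected number of urine events, so the number of participants affected cannot be estimated. There is no effect on PVR, sample size or power.

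The conclusion rests on the protocol text alone. The portal guidance could change what sites do in practice, but not what the protocol says.

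**What to change.** In Table 16-4, restrict the two creatinine criteria to serum events. Add a closing criterion for urine events: the triggering finding, measured by dipstick or by the UPCR or UACR already listed in Section 8.4.1, has returned to baseline or stabilized, within limits set by the medical team. State that this also applies to events first seen at Week 25 or EOS, and check that the portal guidance agrees.

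The cost is one or two lines in Appendix 3 and a few repeat urine tests in participants with an open urine event, some of them after EOS. All the tests are already in the protocol.
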